9.2 Primary Endpoint: Sensitivity Analysis

QFT conversion is detected at fixed timepoints when samples are collected at in-person visits at the study sites. However, conversion may actually occur any time in the interval between planned visits. Interval censoring will be used as sensitivity analysis (based on sustained conversion) using the PROC ICPHREG procedure in SAS (Appendix 7) and data from the mITT efficacy population.

Left censoring duration in days or months is derived from the date of initial conversion. Right censoring duration in months is derived from the date of initial conversion. Left and right censoring values are dependent on the visit at which the event is identified.

Visit at Which Primary Event Identified	Visit Associated with Left Censoring Value	Visit Associated with Right Censoring Value
M6	Day 71*	M6
M12	M6	M12
M18	M12	M18
M24	M18	M24
M30	M24	M30
M36	M30	M36
M42	M36	M42
M48	M42	M48

 Table 3.
 Interval Censoring Information

* Note: If Day 71 was missed, the first in-person visit post Day 71.

For participants who did not experience a conversion, the left censoring value will be equal to the duration from the Day 71 visit (or, if missed, the first in-person visit post Day 71) and the right censoring value will be missing.

A hazard ratio estimate, 95% CI, and p-value will be obtained from this interval censoring procedure and summarized in tables. Vaccine efficacy and associated 95% CI's will also be estimated based on these results.

To assess the rate of early infections, a summary of the number of participants who had positive QFT results at Day 71 (and were therefore excluded from the primary mITT analyses) will also be generated by the treatment group.

9.3 Secondary Analyses

To address the secondary objectives (sustained QFT conversion based on positive QFT test results in participants with a follow-up of 36- and 48-months post vaccination), two analyses will be performed to assess the durability of efficacy against sustained *Mtb* infection post vaccination.

The first secondary analysis will be performed subsequent to or at the same time with the primary analysis after all participants have had at least 36 months of follow-up (or prematurely discontinued), and the second secondary (i.e., final) analysis will be performed subsequent to the initial and the 36-month analysis after all participants have 48 months of follow-up (or prematurely). Both analyses will be based on the mITT efficacy population.

Log-rank tests, stratified by sex and age group (10-11 years old, 12-14 years old, and > 14 years old), will be used to evaluate differences in the distributions of event times between the BCG vaccination and placebo groups. Hazard ratios and 95% confidence intervals will be estimated using stratified Cox proportional hazards regression models.

If the one-sided p-value after all participants have 36 months of follow-up is less than or equal to 0.025, durability after all participants have 48 months of follow-up will be assessed. As such, durability after all participants have reached 36- and 48-months of follow-up will only be concluded if statistically significant differences in event times between the BCG vaccination and placebo arms were met at all prior time points evaluated. Failure to meet the primary or 36- month durability hypothesis will not result in a formal early stopping of the study.

9.4 Exploratory Analyses

The exploratory QFT endpoints (Section 4.3.3) will be analyzed in a manner similar to the primary endpoint.

The following summary results will be presented:

- Analyses based on the 4.0 IU/mL threshold for the initial QFT conversion where initial QFT conversion corresponds to the first QFT conversion after a negative (at or after Day 71) test result. These will be performed for both mITT and PP efficacy populations.
 - ↔ Overall initial QFT conversion rates and incidence rates, with 95% CIs for each treatment group.
 - A Kaplan-Meier plot by treatment group displaying the time to initial conversion based on 4.0 IU/mL threshold, displayed in months, measured from the vaccination date. Participants with no conversion will be censored at the date of data cut-off.
- Analyses based on a range of thresholds for the initial conversion from 0.36 IU/mL to 10 IU/mL using mITT population only.
 - Overall initial conversion rates with 95% CIs for each treatment group will be calculated for threshold values at each 0.01 increment from 0.36 IU/mL to 10

IU/mL. These pointwise estimates and 95% CIs will be plotted for the entire range of threshold values examined. A tabular presentation of the estimated conversion rates and 95% CIs will be displayed for threshold values of 0.36 IU/mL, 0.40 IU/mL, 1.0 IU/mL, 2.0 IU/mL, 3.0 IU/mL, 4.0 IU/mL, 5.0 IU/mL, 6.0 IU/mL, 7.0 IU/mL, and 10.0 IU/mL.

- ↔ Overall sustained conversion rates with 95% CIs for each treatment group will be calculated based on the subset of sustained conversion events identified in the primary analysis for which the initial conversion would have been "positive" using each alternative threshold value ranging from 0.36 IU/mL to 10 IU/mL. A tabular presentation of the estimated rates and 95% CIs will be displayed for the same threshold values as noted above for initial conversions.
- End of trial conversion rates with 95% confidence intervals for each treatment group, where end of trial conversion is defined as QFT conversion from a negative to positive (as per QuantiFERON-TB Gold Plus Package Insert) test result any time post-Day 71 with all QFT results after the initial conversion also positive.
- Kaplan-Meier plots for time to time to end of trial conversion, with tick marks to identify censored observations by treatment group
- Early QFT Reversion rates with 95% confidence intervals for each treatment group will be presented.

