4.2.4 Final Analysis

A final analysis will be performed after all participants have either 48 months of follow-up or completed/prematurely discontinued the study, all safety clinical assessments and concomitant medication data through to the final study visits have been entered and reviewed and all queries related to the data have been addressed.

Additional exploratory analyses including but not limited to host characteristics, *Mtb* isolate characterization, correlate of protection (CoP) and correlate of risk (CoR) analyses may be conducted separately by Gates MRI. These exploratory analyses are outside the scope of this SAP, hence no details for these analyses are described in this document.

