4.3.2 Secondary Efficacy Endpoint

For the secondary efficacy objective (durability of efficacy at 36 months and at 48 months), the endpoints are defined as for the primary efficacy endpoint (i.e., sustained QFT conversion [Section 4.3.1]).

Two mITT durability analyses will be performed: the first one after all participants have at least 36 months of follow-up (or have discontinued the study early) and the second one at study completion when all participants have 48 months of follow-up (or have discontinued the study early) (Section 9.3). For the secondary analysis after 36 months of follow-up, all participants will have a data cutoff date corresponding to their Month 36 visit date or their early discontinuation date if it occurred prior to Month 36 visit.

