7.8 Multiplicity

The primary analysis will be triggered when at least N=118 sustained *Mtb* infection events (defined as QFT conversion from a negative to positive test result, as per QuantiFERON-TB Gold Plus Package Insert) in the mITT efficacy population have accrued.

The primary efficacy endpoint (Section 4.3.1) will be analyzed using a log-rank test, stratified by sex and age group (10-11 years old, 12-14 years old, and >14 years old) to evaluate differences in the distributions of event times between the BCG vaccination and placebo groups. The two durability analyses will be performed: the first one after all participants in the mITT efficacy population have either prematurely discontinued the study or have at least 36 months of follow-up (secondary analysis; a data cutoff date will be established at the date of each participants Month 36 visit) and the second one after all participants in the mITT efficacy population have completed 48 months of follow-up at the end of study (final analysis).

Therefore, the following null hypotheses: $H_{01} \rightarrow H_{02} \rightarrow H_{03}$ will be assumed:

- H_{01} corresponding to the primary analysis (at least N=118 sustained QFT conversion events in the mITT efficacy population have accrued): $S_{s,BCG}(t) = S_{s,Pbo}(t)$
- H_{02} corresponding to the secondary analysis (when all participants have prematurely discontinued the study or have at least 36 months of follow-up): $S_{s,BCG}(t) = S_{s,Pbo}(t)$
- H₀₃ corresponding to the final analysis (when all participants have prematurely discontinued the study or have completed the study with 48 months of follow-up): S_{s,BCG}(t) = S_{s,Pbo}(t)

for strata s=1, 2, ..., 6 (6 strata = sex and age group [10-11 years old, 12-14 years old, and >14 years old]), where S(t) is the survival probability (probability that a participant's time to sustained *Mtb* infection > t).

To account for multiple testing, a step-down approach will be used to preserve the overall Type I error at a one-sided 2.5%. Specifically, if the one-sided p-value associated with the primary hypothesis H_{01} of BCG vaccine efficacy relative to placebo (p_1) is less than or equal to 0.025, the durability of the vaccine efficacy after all participants have 36 months of follow-up (H_{02}) will be formally assessed. If both H_{01} and H_{02} are rejected at one-sided 2.5% then the H_{03} will be formally assessed at one-sided 2.5%.

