9 EFFICACY ANALYSES

9.1 **Primary Analysis**

The primary efficacy endpoint will be analyzed when at least N=118 sustained *Mtb* infection events (defined as QFT conversion from a negative to positive test result, as per QuantiFERON-TB Gold Plus Package Insert) in the mITT population have accrued.

The primary efficacy endpoint (sustained QFT conversion as defined in Section 4.3.1) will be analyzed using a log-rank test, stratified by sex and age group (10-11 years old, 12-14 years old, and >14 years old) to evaluate differences in the distributions of event times between the BCG vaccination and placebo groups.

Censoring and event times will be defined as follows:

- For participants with sustained QFT conversion (censor = 0), time to event will be derived in days as (date of initial conversion date of Day 71 +1) and converted to months. Note that Day 71 here refers to either Day 71 or, if missed, the first in-person visit after Day 71. Date of initial conversion = date of a positive QFT test observed after a negative result at Day 71 or after a negative test at the first in-person visit after Day 71 if the Day 71 visit was missed.
- For participants without sustained QFT conversion (censor = 1), censoring time will be derived in days as (censoring date date of Day 71 + 1) and converted to months. Again, Day 71 refers to either Day 71 or, if missed, the first in-person visit after Day 71.

The censoring date for participants without sustained QFT conversion is the last date at which a non-missing QFT result is available prior to the date of data cut-off. There are several scenarios in which participants may have an initial QFT conversion but fail to meet the requirements for sustained QFT conversion due to subsequent negative, missing, or indeterminate QFT results. Appendix 6 provides details on derivation of event and censoring times for all the expected possible scenarios.

Conventions for additional scenarios not covered in Appendix 6, but based on actual data may need to be considered and detailed in the ADaM specifications prior to all planned analyses. An indeterminate test result will be interpreted as negative for the derivation of a participant's time to event.

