Appendix 5 Prior and Concomitant Medications Date Imputation

Appendix 6 Time to Event Derivation Details

Initial QFT Conversion/ Month 3 post initial conversion/Month 6 post initial conversion ¹	Event/ Censored	Date of Event/Censoring
Sustained conversion prior to date of data cut-off (i.e. Positive/Positive/Positive: -/-/-//+/+/+/any/any)	Event	Date of Initial Conversion to QFT positive
No initial conversion prior to date of data cut-off (-/- /-//-/-)	Censored	Minimum (date of last non-missing QFT result, date of data cut-off)
Initial converters with a 3-month positive QFT and missing 6-month results prior to date of data cut-off (i.e. Positive/ Positive/missing: -/-/-//+/+/- /+/+/Missing)	Censored	Date of initial conversion to QFT positive
Initial converters with a 3-month negative QFT and missing 6-month result prior to date of data cut-off (i.e. Positive/ Negative/Missing: -/-/-//+/-/Missing)	Censored	Date of initial conversion to QFT positive
Initial converters with a missing 3-month and positive 6-month result prior to date of data cut-off (i.e., Positive/Missing/Positive: -/-//+/Missing/+)	Censored	Date of initial conversion to QFT positive
Initial converters with a missing 3-month and negative 6-month results prior to date of data cut-off (i.e. Positive/Missing/Negative: -/-/-//+/Missing/-)	Censored	Date of initial conversion to QFT positive
Initial converters with missing 3-month and missing 6-month results prior to date of data cut-off (i.e., Positive/Missing/Missing: -/-/- //+/Missing/Missing)	Censored	Date of initial conversion to QFT positive

¹indeterminate QFT results are counted a negative test result.

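### SAP 9.4 censors non-converters in the exploratory 4 IU/mL Kaplan-Meier plot at the data cut-off, against the last-QFT rule of SAP 9.1 and Appendix 6

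*SAP*

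**What the plan says.** SAP 9.4 opens with a general rule: "The exploratory QFT endpoints (Section 4.3.3) will be analyzed in a manner similar to the primary endpoint". Its bullet on the 4 IU/mL Kaplan-Meier plot then sets a specific one: "Participants with no conversion will be censored at the date of data cut-off". That plot shows time to initial conversion, measured from vaccination. Under SAP 4.3.3 the endpoint is evaluated at the primary, secondary and final analyses.

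The primary endpoint is handled differently:

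- SAP 9.1: "The censoring date for participants without sustained QFT conversion is the last date at which a non-missing QFT result is available" before the cut-off.
- SAP Appendix 6, row for participants who never convert: "Minimum (date of last non-missing QFT result, date of data cut-off".
- SAP 9.1, later, describing the summary of censoring reasons, also mentions discontinuers being censored at their discontinuation date.

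On observation, SAP 9.2 states: "QFT conversion is detected at fixed timepoints when samples are collected at in-person visits at the study sites".

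The SAP gives a form for the cut-off only for the Month 36 analysis. SAP 4.3.2 says that "all participants will have a data cutoff date corresponding to their Month 36 visit date or their early discontinuation date" if that came earlier, and SAP 7.8 says that "a data cutoff date will be established at the date of each participants Month 36 visit". For the final analysis SAP 4.2.4 gives only the trigger: "A final analysis will be performed after all participants have either 48 months of follow-up or completed/prematurely discontinued the study". SAP 4.2.1 likewise gives only the 118-event trigger for the primary analysis.

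**The concern.** After a participant's last QFT no conversion can be recorded. Someone who leaves the trial but is carried to the cut-off stays in the risk set as conversion-free while untested. The denominators at later visits are then too large, and cumulative conversion is understated. Censoring at the last QFT avoids this.

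The plot serves the first exploratory objective. SAP 9.1 also plans a Kaplan-Meier plot of initial conversion by the package-insert definition. If that plot follows Appendix 6, the two curves would rest on different censoring rules and could not be compared directly. SAP section 6, which lists departures from the protocol, mentions only the removal of the ITT population, so nothing there marks the different rule as deliberate.

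**Working it through.** **The plan's own figure.** The documents give no figure for this curve. Their one related design figure reproduces: 4 × (1.960 + 1.282)² / (ln 0.55)² = 117.6, rounded up to 118 events. It does not depend on this rule.

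**Inputs.**

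- Loss 5% per year (Protocol 9.2).
- QFT at Day 71 and every 6 months to Month 48 (Protocol 8.1.1).
- Conversion hazard h = 0.03, 0.05 or 0.08 per year. This is assumed: Protocol 9.2 expects 8-10% per year in the placebo arm at the package-insert threshold, and no rate is given for 4 IU/mL.
- A common calendar cut-off. This is assumed: no section states one.

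**Formulas.** Let t₀ = 70/365.25 = 0.192 years (negative qualifying test) and tₖ = 0.5, 1.0, …, 4.0 years (visits). The chance that conversion is first detectable at visit k is

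pₖ = exp(−h(tₖ₋₁ − t₀)) − exp(−h(tₖ − t₀)).

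- Last-QFT rule, with loss independent of conversion: 1−KM = Σ pₖ = 1 − exp(−h(t − t₀)).
- Common cut-off: drop-outs never leave the risk set, so 1−KM = Σ pₖRₖ. Here Rₖ = 0.95^(tₖ − t₀) if loss is counted from Day 71, or 0.95^tₖ if counted from vaccination.

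**Worked case, h = 0.05, Month 48, loss from Day 71.** Last-QFT rule: 1 − exp(−0.05 × 3.808) = 17.34%. Common cut-off, in percentage points over the eight visits: 1.506 + 2.332 + 2.217 + 2.108 + 2.004 + 1.905 + 1.811 + 1.721 = 15.60%. The relative shortfall is 1 − 15.60/17.34 = 10.0%.

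**All cases** (each range runs from loss counted from Day 71 to loss counted from vaccination):

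| h per year | Month | 1−KM, last QFT | 1−KM, common cut-off | Relative shortfall |
|---|---|---|---|---|
| 0.03 | 36 | 8.08% | 7.44-7.37% | 7.9-8.8% |
| 0.05 | 36 | 13.10% | 12.07-11.95% | 7.9-8.8% |
| 0.08 | 36 | 20.12% | 18.56-18.38% | 7.8-8.7% |
| 0.03 | 48 | 10.80% | 9.70-9.61% | 10.1-11.0% |
| 0.05 | 48 | 17.34% | 15.60-15.45% | 10.0-10.9% |
| 0.08 | 48 | 26.26% | 23.68-23.45% | 9.8-10.7% |

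In absolute terms the gap is 0.6-1.7 percentage points at Month 36 and 1.1-2.8 at Month 48.

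**If the plot shows survival.** At Month 48, KM rises from 89.20% to 90.30-90.39%, from 82.66% to 84.40-84.55%, and from 73.74% to 76.32-76.55%. That is about 1-4% too high in relative terms.

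**Checks.**

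- Simulation (600,000 per scenario, one-year entry, loss from Day 71) gives 17.31% against 15.58% at Month 48 with h = 0.05. With a calendar cut-off 42 months after study start it gives 13.09% against 12.06% at Month 36.
- Widening conversion to 0.5-10% per year gives a Month 48 shortfall of 9.5-11.1%, so the unknown 4 IU/mL rate matters little.
- The loss rate matters more. Counted from Day 71, the Month 48 shortfall is 6.0-6.2% at 3% yearly loss and 15.4-15.8% at 8%.

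**Participant-specific cut-off.** If each drop-out's cut-off falls on the last QFT, the two rules give the same curve and the effect is 0%.

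**Between arms.** With a hazard ratio of 0.55, h = 0.05 in placebo and equal 5% loss, the ratio of Month 48 cumulative conversion is 0.0994/0.1734 = 0.573 under the last-QFT rule and 0.0894/0.1560 = 0.573 under the common cut-off. If loss were 4% against 6% per year (hypothetical, without basis in the documents), it would be 0.598 or 0.549.

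**The case against.** The strongest reply is that the only cut-off the SAP describes is participant-specific and ends at discontinuation. SAP 9.1 also speaks of censoring discontinuers at discontinuation, and 9.4 points back to the primary analysis. On that reading, carrying drop-outs to a common date is not the natural interpretation, and the effect may be nil. This stands as a limit on size: the 10-11% belongs to an assumed cut-off, not to anything the SAP states. It does not remove the conflict. The participant-specific form is given for Month 36 only, and the discontinuation date need not be the last QFT date. Protocol 7.3 declares loss to follow-up only after three failed visits, and no rule says how to date it. Participants may also stay on study untested, for example during pregnancy (Protocol 8.2.2) or with telephone contacts (Protocol 7.4.3).

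A second reply is that SAP 9.1 leaves uncovered scenarios to the ADaM specifications. The non-converter is not an uncovered scenario, because Appendix 6 has a row for it. A programmer following 9.4 literally would apply the other rule.

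Third, the percentages describe 1−KM. The SAP writes its hypotheses as survival functions, and the code in Appendix 7 does not ask for a failure plot. This is correct, and it is why the survival-scale figure is given as well.

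**Conclusion.** The stated rule is inconsistent with the rest of the SAP and, followed literally, can keep untested participants at risk as conversion-free. The bias runs towards too little conversion. Its size is nil if each cut-off coincides with the last QFT. With a common date at the primary or final analysis (assumed), 5% yearly loss independent of conversion, and 6-monthly testing, cumulative conversion would be about 8-9% low in relative terms at Month 36 and 10-11% low at Month 48. A survival curve would be about 1-4% too high at Month 48.

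A reader might infer that the efficacy result is biased. The documents do not support that. The sentence belongs to one Kaplan-Meier bullet, SAP 7.8 makes exploratory inference descriptive only, and the primary and secondary analyses have their own censoring rule. With equal loss the between-arm ratio is essentially unchanged. A reader might also take 10-11% as an established error, but no section states the common date on which it depends. Severity is minor.

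**What to change.** In the 4 IU/mL Kaplan-Meier bullet of SAP 9.4, replace the censoring sentence with: *Non-converters are censored at their last non-missing QFT result on or before the data cut-off, following Appendix 6.* This works whatever form the cut-off takes, so the point does not depend on defining the cut-off for the primary and final analyses, although stating it there would help. The vaccination-date origin is an explicit choice and can stay.

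The cost is one SAP sentence and minor programming. The descriptive cumulative curve may read slightly higher; nothing confirmatory changes.

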9.5 Other Exploratory Analyses

The SARS-CoV-2 serostatus will be summarized by time point (calendar month/year) and by treatment group.

Among participants who present with suspected COVID-19, the proportion of participants with positive nucleic acid amplification will be summarized overall, by site, and by treatment group.

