2.1.1. Rationale for addition of COVID-19 related study objectives

The Government of South Africa declared the COVID-19 pandemic a National Disaster on 15 March 2020 and the Sponsor of this study issued a pause for enrollment on 17 March 2020, effective 19 March 2020.

The Government of South Africa subsequently ordered a lockdown (stay-at-home order) for three weeks on 26 March 2020 and subsequently extended it for an additional two weeks, through the end of April, 2020. Under the lockdown, most trial participants are not able to come to the investigational site for protocol-specified visits.

Since 1 May 2020, South Africa has employed a system of alert levels at the provincial and, in some cases, the district level. Criteria based on the rate of infection as well as health system capacity are used by the National Command Council to determine the alert level.

Enrollment into this study can only resume once the Government, local IRBs, investigators, and the sponsor agree that it is acceptable to resume enrollment. Enrollment may also need to be paused again in the future, depending on the COVID-19 situation at national, province and district level.

Study investigators and study sites have defined infection control measures for COVID-19 that need to be implemented prior to resuming enrollment and are consulting with IRBs to determine the conditions that would allow for enrollment to continue.

The study investigators and study sponsor agreed to add two exploratory COVID-19 endpoints to this study. Firstly, in order to describe COVID-19 among the study population, to differentiate COVID-19 from pulmonary TB, and to minimize risks to participants and staff, a diagnostic test for SARS-CoV-2 (based on nucleic acid amplification) will be performed if a participant presents with suspected COVID-19. A description of the frequency and symptomatology of

COVID-19 by treatment group is of great scientific interest as BCG-induced trained immunity has been hypothesized to potentially offer protection from progression to severe COVID-19. BCG vaccination is currently being tested as a prophylactic intervention against COVID-19 (NCT04327206 and additional studies).

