7.4.4. Addition of exploratory objectives and endpoints related to COVID-19

The following exploratory objectives were added:

- To describe COVID-19 among study participants who present with suspected COVID-19
- To describe the serostatus of SARS-CoV-2 infection.

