9.4.3.2. Other Exploratory Analyses

The SARS-CoV-2 serostatus will be summarized overall, as well as by time and treatment group. Among participants who present with suspected COVID-19, the proportion of participants with positive nucleic acid amplification will be summarized overall and by treatment group. Signs and symptoms of disease will be described for each participant.

Further exploratory analyses related to host characteristics and responses to vaccination and or *Mtb* infection will also be examined. Specific objectives and hypotheses related to these analyses will be documented and reported in a separate scientific and statistical analysis plan prior to full unblinding and analysis of data associated with these exploratory analyses.

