To assess the immunogenicity of BCG revaccination	Frequency of Mtb- , BCG- and/or non-tuberculous mycobacteria (NTM)-specific cluster of differentiation (CD)4 T cells expressing one or more cytokines, e.g., IFN- γ , tumor necrosis factor (TNF)- α , interleukin (IL)-2 and/or IL-22 by intracellular cytokine staining (ICS).
To describe host attributes and host responses	Genetic markers and sequences
To describe host attributes and host responses following QFT conversion	Transcriptomics and gene expression markers Proteomics
To explore and/or develop candidate correlates	Antibody analyses
of risk (CoRs) and correlates of protection (CoPs)	Cellular analyses (e.g., natural killer cells [NK cells], B cells, T cells, myeloid cells)
To detect and describe incident tuberculosis	Incidence of laboratory-confirmed TB disease
To characterize Mth isolates	Signs & symptoms of incident TB disease
TO CHARACLEFIZE INILD ISOIALES	Mtb drug sensitivity and/or Mtb genetic markers
To describe (Coronavirus Disease 2019) COVID-	Signs and symptoms of illness, by treatment group
19 among study participants who present with suspected COVID-19	SARS-CoV-2 nucleic acid amplification from nasal or or oropharyngeal sample
To describe the serostatus of Severe Acute Respiratory Syndrome-Coronavirus-2 (SARS- CoV-2) infection	Serological test results for SARS-CoV-2, by treatment group

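### Test-confirmed COVID-19 by arm is summarised only as the NAAT-positive share of suspected cases, a denominator formed after vaccination that does not give the frequency by treatment group

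*SAP*

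**What the plan says.** SAP 9.5 gives the only by-arm summary of test-confirmed COVID-19: "Among participants who present with suspected COVID-19, the proportion of participants with positive nucleic acid amplification will be summarized overall". The sentence goes on to add breakdowns for each site and each arm. Protocol 9.4.3.2 has the same conditional summary: "the proportion of participants with positive nucleic acid amplification will be summarized overall and by treatment group". Under protocol 7.4.4.2 the test is done when a participant presents with symptoms such as fever, respiratory illness or loss of smell.

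The rationale in protocol 2.1.1 is wider. It begins "A description of the frequency and symptomatology of" COVID-19 and continues "by treatment group is of great scientific interest as BCG-induced trained immunity has been hypothesized to potentially offer protection from progression to severe COVID-19". The formal objective in protocol 7.4.4 is narrower: "To describe COVID-19 among study participants who present with suspected COVID-19".

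Two nearby summaries do not use the suspected-case denominator. SAP 9.5 tabulates SARS-CoV-2 serostatus by calendar time and arm. SAP 11.1 tabulates COVID-like symptoms over the preceding six months by arm in the Safety population. SAP section 3 also lists the endpoint "Signs and symptoms of illness, by treatment group", for which SAP 9.5 specifies no analysis.

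**The concern.** A frequency by treatment group needs the number vaccinated in each arm, or their follow-up time, as its denominator. The planned percentage uses the participants who presented instead. Presentation comes after vaccination, and it can differ by arm in two ways. BCG may change how often participants become ill, with COVID-19 or with something else. Also, protocol 6.3.2 accepts that participants and site staff learn the allocation when a BCG lesion appears, which may change reporting and suspicion.

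Between arms, the share therefore mixes any effect on COVID-19 with any difference in other suspected illness. At stake is how one exploratory table is read. A reader who takes the percentage as the comparison that protocol 2.1.1 calls for could miss a difference or see one that is not there.

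**Working it through.** The plan states no COVID-19 figure, so there is nothing to reproduce; the 118-event calculation does not bear on this point.

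**Inputs.** N = 900 per arm (SAP 7.2). The risks below are assumptions, because the documents give none. C is the placebo-arm risk of a NAAT-positive suspected illness, and O is the risk of any other suspected illness, with each participant counted once. R_C and R_O are the BCG:placebo risk ratios for C and O. The 45% reduction borrows the size of the primary efficacy assumption for illustration only.

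**Formulas.**
- Planned share: C/(C+O) for placebo and R_C·C/(R_C·C + R_O·O) for BCG.
- Share ratio: R_C·(C+O)/(R_C·C + R_O·O).
- Ratio per vaccinated participant: R_C.

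**Worked case, C = 5%, O = 15%.** Placebo has 45 positives among 180 suspected cases, or 25.0%, and 45/900 = 5.0% of those vaccinated.
- Both reduced 45%: BCG 24.75/99 = 25.0%, share ratio 1.00. Per vaccinated participant, 24.75/900 = 2.75%, ratio 0.55.
- Only other illness reduced 45%: BCG 45/119.25 = 37.7%, share ratio 1.51. Per vaccinated participant, ratio 1.00.

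**All settings (share ratio):**

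| Scenario | R_C (true ratio) | R_O | C 5%, O 15% | C 10%, O 20% | C 10%, O 10% |
|---|---|---|---|---|---|
| A. Both reduced 45% | 0.55 | 0.55 | 1.00 | 1.00 | 1.00 |
| B. Only other illness reduced 45% | 1.00 | 0.55 | 1.51 | 1.43 | 1.29 |
| C. Only COVID-19 reduced 45% | 0.55 | 1.00 | 0.62 | 0.65 | 0.71 |
| D. Only other illness reduced 30% | 1.00 | 0.70 | 1.29 | 1.25 | 1.18 |
| E. Only other illness raised 50% | 1.00 | 1.50 | 0.73 | 0.75 | 0.80 |

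Row E, last column, in full: 0.10/0.20 = 0.50 against 0.10/0.25 = 0.40, ratio 0.80.

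**Do other planned tables fill the gap?**
- Serostatus (SAP 9.5) describes infection, not illness.
- COVID-like symptoms (SAP 11.1) are unconfirmed. They sit under Medical History, and it is unclear how far they cover time after vaccination.
- Adverse event tables (SAP 10.1) stop at 28 days for unsolicited events and Month 6 for serious ones.
- COVID-19 outputs for the IDMC (SAP 4.2.3) are participant listings.
- The default denominator (SAP 7.3) is participants with non-missing data, which for NAAT means those tested.

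So no planned table gives confirmed COVID-19 over a randomised or Safety denominator through follow-up. SAP 10.9 already does this for tuberculosis: suspected cases as a percentage of those still in the study, and confirmed cases per duration of follow-up, by arm.

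**The case against.** The strongest reply is that SAP 9.5 does what the objective asks. The objective is exploratory, is worded for those who present with suspected disease, and has no between-arm test attached; SAP 7.8 makes any exploratory inference descriptive. This stands. The mismatch is with the rationale in protocol 2.1.1, not with the objective.

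Second, a reader might infer that a real effect would vanish from the output. It would not quite: SAP 7.3 shows n with each percentage. The worked case for scenario A would print as about 45/180 against 25/99, and with 1:1 allocation the positive counts can be compared. What is missing is a population denominator, a rate and an interval.

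Third, the share has one merit. If the arms differ only in willingness to present, by a common factor a, then a·C/(a·C + a·O) = C/(C+O). The share is unaffected, while n/N is biased by a. Because the test is done only on presentation, a Safety denominator reduces the problem without removing it. This is a reason to report both.

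Three stronger readings are not supported:
- That COVID-19 by arm is described in no other way: serostatus and symptoms are also tabulated by arm.
- That the hypothesis is protection from respiratory illness in general: protocol 2.1.1 speaks of progression to severe COVID-19, which none of these tables measures.
- That the amendment was written for this comparison: protocol 7.4.1 describes changes needed to continue the study in the pandemic, and protocol 2.1.1 also gives the test diagnostic and risk-reduction purposes.

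**Conclusion.** The point holds for test-confirmed COVID-19. Its only planned by-arm summary conditions on a group formed after vaccination and does not give the frequency by arm described in protocol 2.1.1. Under the assumed risks, a true ratio of 0.55 can show as 1.00 (scenario A) or be diluted to 0.62–0.71 (scenario C). A true ratio of 1.00 can show as anything from 0.73 to 1.51 (scenarios B, D and E). These sizes are illustrative; the mechanism needs only that the incidence or reporting of other suspected illness differs by arm, or that COVID-19 and other illness are affected together.

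The consequence is small. It concerns one exploratory table whose counts allow partial recovery, and no primary, secondary or safety conclusion is affected.

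**What to change.** In SAP 9.5, for all Safety-population participants by arm, add:
- n/N (%, 95% CI) and rate per person-time with at least one NAAT-positive episode;
- n/N presenting with suspected COVID-19, and n/N tested.

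Start person-time at the later of Day 1 and the start of SARS-CoV-2 testing in the trial. Protocol 7.4.1 records 349 participants vaccinated before the March 2020 pause, and the test was added only with Version 5 of May 2020, so counting from Day 1 would include time when no case could be confirmed.

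Keep positivity among suspected cases as a secondary descriptor. Footnote that only presenting cases are captured and that presentation may differ by arm because the BCG lesion can unblind. While the section is open, specify the by-arm summary of signs and symptoms that SAP section 3 lists as an endpoint.

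The cost is a revised table shell and a documented start date for testing. The data are already planned for collection, and the tuberculosis summaries in SAP 10.9 offer a template.
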